10.4.2.2 Adverse events

Data handling

AEs will be coded using the latest version of the MedDRA and graded using the CTCAE version 4.03. The CTCAE grade 5 (death) will not be used in this study.

[figure not shown]
A patient with multiple CTCAE grades for an AE will be summarized under the maximum grade recorded for the event. A subject with multiple occurrences of an AE is counted only once in the AE category (e.g. system organ class, preferred term).

[figure not shown]

10.4.2.3 Laboratory parameters

Data handling

All laboratory values will be converted into SI units, as appropriate, and the severity grade calculated using CTCAE, version 4.03. For laboratory tests covered by CTCAE, a Grade 0 will be assigned for all non-missing values not graded as 1 or higher. Grade 5 will not be used. For laboratory tests where grades are not defined by CTCAE, results will be graded by the low/normal/high classifications based on local laboratory normal ranges. The list of parameters with CTCAE grading and LNR is presented in [Section 10.5.3](#). 

[figure not shown]

10.4.2.4 Electrocardiograms

Data handling

- Unscheduled ECGs are included in the analysis of notable value.
- Triplicate 12 lead sequential readings will be performed at baseline and post-baseline for a patient at the given time points ([Section 7.2.2.6](#)), all individual values are transferred, in which case, ECGs are averaged over the patient and then across patients for change from baseline analysis.
- No adjustment (in the variance) is made to account for different patients having differing number of ECGs being averaged at a given time point. (It is assumed that the scheduled assessments for each patient are the same and any deviations are sporadic and minor).

10.4.2.5 Vital signs

Data handling

Change from baseline will only be summarized for patients with both baseline and post-baseline values.

10.4.2.6 Tolerability

Tolerability of study drug treatment will be assessed by summarizing the number and percentage of dose interruptions and dose reductions per patient, together with reasons for dose interruption and dose reductions. Dose intensity and relative dose intensity of LTT462 per patient will be summarized. For relative dose intensity, the number and proportion of patients within the following categories will be presented: < 0.5 , $\geq 0.5 - < 0.75$, $\geq 0.75 - < 0.9$, $\geq 0.9 - < 1.1$ and ≥ 1.1 .

10.4.3 Handling of missing values/censoring/discontinuations

No imputation for missing data will be performed. Patients with missing baseline assessments will be excluded from analyses where a baseline value is required to compute the corresponding endpoint.

10.4.4 Supportive analyses

During the course of the study, additional analyses may be identified based on emerging safety data, to support the primary analyses. These analyses will be defined in the statistical analysis plan prior to clinical database lock.

10.5 Secondary objectives

[figure not shown]
10.5.1 Secondary efficacy objectives

Tumor response will be determined locally according to RECIST v1.1 (refer to [Appendix 1](#)) per local investigators' assessment. The FAS will be used for all efficacy analyses.

Efficacy endpoints are progression free survival (PFS), ORR, duration of response (DOR), and DCR. [REDACTED]

Dose escalation part

For the dose escalation part, the best overall response (BOR) and individual lesions, and the PFS time will be presented for each patient in a listing.

10.5.2 Secondary Safety objectives

10.5.2.1 Analysis set and grouping for the analyses

For all safety analyses, the safety set will be used. All tables will be presented by treatment group for the dose escalation part and by study group for the dose expansion part.

The overall observation period will be divided into three mutually exclusive segments:

- pre-treatment period: from day of patient's informed consent to the day before first dose of study medication
- on-treatment period: from day of first dose of study medication to 30 days after last dose of study medication
- post-treatment period: starting at day 30+1 after last dose of study medication.

10.5.2.2 Adverse events (AEs)

Analysis of adverse events will be described similar to the primary endpoint. Summary tables for adverse events (AEs) will include only on-treatment events. The listing of all AE will include all AE reported in the study, without date restrictions.

The incidence of the following treatment-emergent adverse events will be summarized by maximum severity (based on CTCAE grades), system organ class and/or preferred term: AE suspected to be study drug related, AE leading to study drug discontinuation, AE requiring drug dosage adjustments/temporarily interrupted, SAE suspected to be study drug related.

[figure not shown]
Deaths with onset on-treatment and also all deaths occurring during the study will be summarized by system organ class and/or preferred term. AE which are not SAE will be summarized by primary system organ class and preferred term.

LTT462 specific safety event categories (SEC) may be considered. Such categories consist of one or more well-defined safety events which are similar in nature and for which there is a specific clinical interest in connection with the study treatment.

For each specified SEC, number and percentage of patients with at least one event part of the SEC will be reported.

10.5.2.3 Laboratory abnormalities

[figure not shown]
All laboratory values will be converted into SI units, as appropriate, and the severity grade calculated using CTCAE, version 4.03. Data handling will be as described in [Section 10.4.2](#). Analysis of chemistry and hematology tests results are described in [Section 10.4.2](#). A listing of patients with abnormal values of CTCAE grade 3 or 4 will be presented (for all laboratory parameters measured). For parameters (independent of the test category) with no CTCAE grade, a listing of patients with abnormal values will be provided, with low/high values flagged. ■■■■■

10.5.2.4 Hepatic abnormalities

[figure not shown]
Hepatic abnormalities will be assessed based on the following liver function tests: ALT, AST, ALP, and total bilirubin (TBL). The number and percentage of patients with newly occurring

notable hepatic laboratory values within the categories presented below will be provided. For the combined criteria, shift tables to compare baseline to the worst post-baseline will be presented. A listing of patients with at least one newly occurring notable event will be provided.

10.5.2.5 Other safety data

Other safety assessments include ECOG performance status, physical examinations, height, pregnancy test, MUGA scan or ECHO, 

10.5.2.6 Supportive analyses for secondary objectives

Refer to [Section 10.4.4](#).

10.5.3 Pharmacokinetics

Pharmacokinetic parameters will be determined by non-compartmental method(s) using the pharmacokinetic profile of LTT462. PK parameters listed in [Table 10-7](#) will be derived and reported, when feasible.

Further analyses may be conducted using population PK approaches. In addition, a model based approach may be used to explore the potential relationship between efficacy, safety, and/or biomarker endpoints and LTT462 concentration and/or exposure metrics. Any analyses performed will be specified either in the study analysis plan or in a stand-alone analysis plan document. All analyses will be reported either in the CSR or a stand-alone report.

Table 10-7 Noncompartmental pharmacokinetic parameters

AUC _{last}	The AUC from time zero to the last measurable concentration sampling time (T _{last}) (mass x time x volume ⁻¹)
AUC _{tau}	The AUC calculated to the end of a dosing interval (tau) at steady-state (amount x time x volume ⁻¹)
AUC _{inf}	The AUC from time zero to infinity (mass x time x volume ⁻¹)
C _{max}	The maximum (peak) observed plasma, blood, serum, or other body fluid drug concentration after single dose administration (mass x volume ⁻¹)
T _{max}	The time to reach maximum (peak) plasma, blood, serum, or other body fluid drug concentration after single dose administration (time)
C _{min}	Observed concentration at the end of a dosing interval (taken directly before next administration)
CL/F	The total body clearance of drug from the plasma (volume x time ⁻¹)
Racc	Accumulation ratio calculated using AUC _{tau} at steady state divided by AUC _{tau} at Day 1
T _{1/2}	Effective elimination half-life

10.5.3.1 Data handling principles

All concentrations below the lower limit of quantitation (LLOQ) or missing data will be labeled as such in the concentration data listings. Concentrations below the LLOQ will be treated as zero in summary statistics and for the calculation of pharmacokinetic parameters, unless otherwise stated under the Pharmacokinetic Analysis Set.

At the time of analysis, concentration data from patients may be removed from the estimation of certain PK parameters depending on the number of available blood samples, concomitant medications, vomiting, etc. Specific time points might be removed from the analysis set if

technical issues with the sample are reported (e.g. sampling issues, missing information). These patients and concentration data points will be identified at the time of analysis

10.5.3.1.1 Data analysis set

All pharmacokinetic data analyses and PK summary statistics will be based on PAS. Only PK blood samples with date and time and for which the last prior dose dates and times are adequately recorded will be included in the PK analyses.

10.5.3.1.2 Basic tables, figures, and listing

[figure not shown]
Descriptive statistics such as arithmetic and/or geometric mean and CV%, median and range, will be presented for all pharmacokinetic parameters, as applicable. Zero concentrations will not be included in the geometric mean calculations. T_{max} will be summarized in terms of median values and ranges. Missing concentrations or PK parameter values will not be imputed. A listing of derived PK parameters per patient will be produced by treatment group.

Mean plasma concentration versus time profile plots will be generated for LTT462. Further graphical exploratory analyses (such as individual plasma concentration versus time) will be carried out if deemed appropriate.

10.5.3.2 Dose proportionality

[figure not shown]
The analysis of dose proportionality will be conducted for AUC and C_{max} of LTT462 using a power model on log-transformed scale. The log-transformed PK parameters will each be regressed onto a fixed factor for log (dose). The 90% confidence interval (CI) of the slope for each PK parameter will be computed from the model and presented in a summary table. Dose-proportionality will only be investigated if at least three doses of LTT462 are investigated.

Exploratory analysis will be carried out if deemed necessary.

10.5.3.4 Time-dependency

If AUC_{inf} can be reliably estimated on Day 1, the time dependence of the PK (comparison within subject of Day 1 AUC_{inf} with Day 15 AUC_{tau} with point estimates and CI) will be analyzed. Details will be included in the study analysis plan.

10.5.4 Biomarkers

Since this clinical trial was not designed to address specific biomarkers-related hypotheses, the analysis of this data should be viewed as [REDACTED] hypotheses generating.

Secondary objectives include the assessment of the PD effect of LTT462 in both tumor and blood of LTT462. For assessment of PD effects of LTT462 in tumor, pre- and post- treatment tumor biopsies will be examined for expression of DUSP6. For assessment of PD effects in blood, levels of DUSP6 will be measured in samples isolated concomitantly with those collected for PK measurements.

10.5.4.1 Outline of the data analysis

Changes in biomarkers in blood and tumor samples may be summarized by means of descriptive analysis and correlation with clinical response and exposure where feasible. If the number of samples is inadequate to perform a rigorous data analysis, then the available data will only be listed.

Additional analyses will be specified in a separate analysis plan and may be reported in the CSR. These analyses may include but are not limited to the meta-analysis of data from this study combined with data from other studies or the analysis of biomarkers generated from samples collected during the study but analyzed after the database lock and completion of the CSR.

10.5.4.2 Data handling principles

For change from baseline analyses, calculations will only be performed on patients with measurable samples and pre- and post- treatment time points. If both the baseline and post baseline values are below the LLOQ, percent change, absolute change, or fold-change from baseline will not be imputed.

10.5.4.3 Data analysis principles

10.5.4.3.1 Analysis sets

The FAS will be used for all biomarker related analyses. The number of patients with measurable samples will be identified in the summaries and relevant proportions will be calculated against this number.

10.5.4.3.2 Basic tables, figures and listings

[figure not shown]
Baseline and percentage change from baseline in delta Ct (Δ CT) values of DUSP6 expression will be summarized by treatment.

A waterfall plot will be used to depict the change from baseline in Δ CT values of DUSP6 expression (both tumor and blood samples) and annotated with the best overall response.

The best percentage change in tumor size and best overall response will also be displayed as a waterfall plot, annotated with MAPK pathway gene alterations at baseline.

[figure not shown]
Change from baseline in Dual Specificity Phosphatase 6 (DUSP6) expression

To assess the drug effect on MAPK signaling and correlation to preliminary anti-tumor response, changes of molecular status of DUSP6 in pre- and post-treatment tumor biopsies and blood samples will be analyzed. Percentage and fold changes will be listed.

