2.14.4.1 Handling of data

Percent Change in DUSP6 Expression is derived from the Relative Expression Ratio (RER), calculated according to the 'Comparative CT Method' described in Applied Biosystems User Bulletin #13 (2001) and consistent with the model described in (Pfaffl and Hageleit 2001). In this method, Δ CT is computed by subtracting the CT of a Reference Gene from the CT of DUSP6 for both Baseline and Post-Baseline Samples. RER is calculated by raising 2.0 to an exponent computed by subtracting the (Δ CT) of the Baseline Sample from (Δ CT) of the Post-Baseline Sample. RER is transformed by subtracting 1.0, such that expression increases and decreases are indicated when %Change is greater than or less than zero, respectively.

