2.14.4.2 Deriving change from baseline in DUSP6 expression

Denoting the baseline (Δ CT) of one patient as **B** and the post-baseline as **PB**, then

• RER = $2^{(B-PB)}$

% Change in expression relative to Baseline = (RER -1)*100

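### The protocol summarises DUSP6 as a percentage change in delta-CT, which is not a valid measure, while the SAP summarises percentage change in expression

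*Protocol*

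**What the plan says.** **Protocol 10.5.4.3.2** describes three DUSP6 outputs.

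- A summary by treatment of "Baseline and percentage change from baseline in delta Ct" values.
- A plot, introduced as "A waterfall plot will be used to depict the change from baseline in" delta-CT values, for tumor and blood and annotated with best overall response. No percentage is mentioned here.
- A listing, under a heading about DUSP6 expression: "Percentage and fold changes will be listed". The scale of these changes is not defined.

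**SAP 2.14.4.1** says that delta-CT is "computed by subtracting the CT of a Reference Gene from the CT of DUSP6 for both Baseline and Post-Baseline Samples", and that "Percent Change in DUSP6 Expression is derived from the Relative Expression Ratio (RER"). It fixes the direction: "expression increases and decreases are indicated when %Change is greater than or less than zero, respectively".

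**SAP 2.14.4.2** sets RER = 2^(B−PB) and gives "Change in expression relative to Baseline = (RER -1)*100". SAP Table 2-10 bases both the DUSP6 summaries and the waterfall plots on expression.

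In the visible text, the SAP does not say that it departs from the protocol statistic. SAP section 5 only refers changes in planned analysis to the study report.

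**The concern.** The two documents give different quantities for one secondary endpoint, and the protocol's quantity is unsound as written. Delta-CT is the DUSP6 cycle threshold minus that of a reference gene. It is therefore already a log2 ratio, and its zero is set by the choice of reference gene. Dividing a change in it by its own baseline makes the result depend on where that zero falls.

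At stake is the reading of the pharmacodynamic summary by dose group. Cohorts in the escalation part have 1 to 6 patients (Protocol 6.2.3.2). Groups with identical suppression could look different in a table of percentage change in delta-CT only because their baseline delta-CT values differ.

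**Working it through.** **Inputs**

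- Delta-CT = CT(DUSP6) − CT(reference gene), from SAP 2.14.4.1. It rises when DUSP6 expression falls.
- SAP measure: S = 100 × (2^(B−PB) − 1), from SAP 2.14.4.2.
- Protocol summary measure: P = 100 × (PB − B) / B. The protocol does not print this formula; it is the ordinary meaning of a percentage change from baseline in delta-CT.
- Protocol waterfall measure: D = PB − B.
- Baseline delta-CT: the documents give no values. Those below are assumed, from −2 to 8 in the table and up to 10 in the later examples.

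The plan states no DUSP6 figure to reproduce.

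**Step 1. The same suppression on each scale.** Take PB = B + 1, one cycle. Then RER = 2^(−1) = 0.5 and S = 100 × (0.5 − 1) = −50% at every baseline, while P = 100 × 1/B.

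| Assumed B | P (protocol table) | D (protocol waterfall) | S (SAP) |
|---|---|---|---|
| −2 | −50% | +1 | −50% |
| 0 | undefined | +1 | −50% |
| 0.5 | +200% | +1 | −50% |
| 2 | +50% | +1 | −50% |
| 4 | +25% | +1 | −50% |
| 8 | +12.5% | +1 | −50% |

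P varies as 1/B. Its sign is opposite to that of S when B > 0 and the same when B < 0.

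**Step 2. Dependence on the reference gene.** Suppose another reference gene shifts every delta-CT by +2. A patient with B = 2 then has B = 4. P moves from +50% to +25%, while D and S do not change.

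**Step 3. Group summary.** Three patients, each suppressed by 50%:

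- B = 2, 5, 10: mean P = (50 + 20 + 10)/3 = +26.7%; mean S = −50%.
- B = −2, 5, 10: mean P = (−50 + 20 + 10)/3 = −6.7%; mean S = −50%.

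**Step 4. Ordering of patients in the percentage table.** A patient with B = 2 and a one-cycle rise (50% suppression) has P = +50%. A patient with B = 10 and a three-cycle rise has S = 100 × (2^(−3) − 1) = −87.5%, but P = 100 × 3/10 = +30%. The more suppressed patient shows the smaller change.

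**Step 5. The waterfall.** Since S = 100 × (2^(−D) − 1), S is a strictly decreasing function of D, and baseline does not enter. The protocol's waterfall therefore ranks patients exactly as the SAP measure does, with the axis reversed.

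**Step 6. The SAP's own exponent.** SAP 2.14.4.1 describes RER as "raising 2.0 to an exponent computed by subtracting the" baseline delta-CT from the post-baseline value, so the exponent is PB − B. For the case in Step 1 that gives 100 × (2^1 − 1) = +100%, an apparent increase under suppression. This contradicts both the formula in SAP 2.14.4.2 and the direction stated in SAP 2.14.4.1 itself. The formula B − PB is the one consistent with that direction.

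**The case against.** The strongest reply is that the SAP settles the matter. It is dated 13-May-2019, after protocol Amendment 3 (13-Mar-2018). It gives an explicit expression-scale formula and bases the DUSP6 tables and waterfalls on expression. On that view the protocol sentence is loose wording, and the protocol's own listing of fold changes, which belong to the expression scale, supports this reading. Much of this stands: the SAP does not list a percentage of delta-CT among its outputs. But the SAP neither withdraws nor acknowledges the protocol statistic, and its two descriptions of RER disagree, so it does not fully cure the conflict.

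Three stronger readings are tempting and are not supported.

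- *The two documents always give opposite signs.* For the percentage table this needs a positive baseline delta-CT and the SAP 2.14.4.2 formula. With a negative baseline the signs agree, and under the SAP 2.14.4.1 wording they agree when baseline is positive. No delta-CT values are given that would settle which case applies.
- *The protocol's waterfall is distorted too.* It plots the absolute change, which is free of baseline and keeps the order of patients (Step 5). Only its direction differs.
- *The recommended dose could be wrong as a result.* Pharmacodynamic data are one of several inputs to the expansion dose (Protocol 4.1.1), with overdose control as the formal constraint (Protocol 10.4.2.1). Protocol 10.5.4 treats the biomarker analyses as hypothesis-generating. Nothing says that dose meetings use a percentage of delta-CT, so this link would be conjecture.

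**Conclusion.** The point holds for the percentage summary table. As written, Protocol 10.5.4.3.2 specifies a statistic that is undefined at a baseline of zero, changes sign with baseline and varies as 1/B. The SAP uses a different and valid one. For a uniform 50% suppression the protocol figure runs from +12.5% to +50% over assumed baselines of 8 down to 2 and is −50% at −2, against a constant −50% under SAP 2.14.4.2.

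The sizes rest on assumed baselines and on the ordinary reading of a percentage change. The dependence on baseline is algebraic and needs no assumed values. The endpoint is descriptive, so no error rate or sample size is affected. This should be corrected, but it does not threaten the primary objective.

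**What to change.** 1. In Protocol 10.5.4.3.2, or as a documented change in the SAP, replace the percentage change in delta-CT with percentage change from baseline in DUSP6 expression, 100 × (2^(B−PB) − 1), defining B and PB as the baseline and post-baseline delta-CT.
2. State in the SAP that a percentage change of delta-CT is not produced.
3. Draw the waterfall on that expression scale, or as a log2 change with its direction labelled.
4. In SAP 2.14.4.1, correct the described exponent to baseline minus post-baseline, to match SAP 2.14.4.2.

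The cost is one sentence in the protocol or a documented SAP change, plus short SAP wording edits. No new data are needed.

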10.5.4.3.3 Advanced analysis methods

Additional analyses that may be performed after the completion of the final CSR will be documented in separate analysis reports. These analyses may include but are not limited to the meta-analysis of data from this study combined with data from other studies or the analysis of biomarkers generated from samples collected during the study but analyzed after the database lock and completion of the CSR. The data analysis will be described in a separate analysis plan document and may be included in the CSR.

10.7 Interim analysis

No formal interim analyses are planned. However, the dose escalation design foresees that decisions based on the current data are taken before the end of the study. More precisely, after

[figure not shown]
each cohort in the dose escalation part, the next dose of LTT462 has to be chosen depending on the observed data. Details of this procedure and the process for communication with Investigators are provided in [Section 6.2.3](#).

[figure not shown]
[figure not shown]
[REDACTED]
[REDACTED]
[REDACTED] Cumulative study data (including safety, tolerability, preliminary anti-tumor activity, PK, and PD) will be reviewed on an ongoing basis by Novartis and study investigators.

10.8 Sample size calculation

10.8.1 Dose-escalation part

Initially, cohorts of 1 to 3 evaluable patients will be enrolled in the dose-escalation part. Upon observation of specific toxicities (see [Section 6.2.3](#) for details), cohorts of 3 to 6 evaluable patients will be enrolled including at least six patients at the MTD/RDE level, as described in [Section 6.2.3](#). Multiple cohorts may be sequentially enrolled to the same dose level. Additional cohorts of 1 to 6 patients may be enrolled at any dose level below the estimated MTD/RDE for further elaboration of safety and pharmacokinetic parameters as required. At least 21 patients are expected to be treated in the dose escalation part, for the model to have reasonable operating characteristics relating to its MTD recommendation. In the event that a lower dose is recommended for the use in the dose expansion without identification of the MTD, then the sample size may be smaller than 21.

11 Ethical considerations and administrative procedures

